7.2.2 Trial Flow Chart

	Visit 1	Visit 2	Visit 3
Procedure Name	Screening period (-7 – 0 days)	FFR - ICA Examination	Follow (48 hours post-surgery follow up)
Sign Informed Consent Form	X		
Demographic Information ¹	X		
Complete Medical History ²	X		
Pregnancy Check-up	X		
Laboratory Examination ³	X		X ⁷
Inclusion /Exclusion Criteria	X ⁴	X ⁵	

	Visit 1	Visit 2	Visit 3
Procedure Name	Screening period (-7 – 0 days)	FFR - ICA Examination	Follow (48 hours post-surgery follow up)
Vital Signs ⁶	X	X	X
Device Information		X	
Investigational Device Coronary Artery FFR Value		X	
Investigational Device Success Rate		X	
Control Group Device Coronary Artery FFR value		X	
Control Group Device Success Rate		X	
Adverse Events	X	X	X
Device Defects		X	X
Combined Medications	X	X	X

Note:

1. Demographic Information: including gender, age (date of birth), ethnicity, height, weight, etc.
2. Complete medical history: inquire and record the subject's past illness, surgical history, current medical history, etc.
3. Laboratory examination: including blood routine (RBC, WBC, PLT), liver function (ALT, AST), kidney function (BUN, CR), myocardial enzyme (cTNT) / cTNI, CK, CK-MB). The laboratory will accept examination results within 7 days of the signing of the informed consent.
4. Visit I Inclusion/ Exclusion Criteria: complete the inclusion criteria item 1 to 4, and exclusion criteria item 1 to

4 and item 10;

5. Visit 2 Inclusion/ Exclusion Criteria: complete the inclusion criteria item 5, and exclusion criteria item 5 to 9
6. Vital signs: record subject's systolic pressure, diastolic pressure and heart rate
7. Visit 3 Laboratory examination completed within 48 hours of surgery. If the cTNT / cTNI and CK-MB exceed the upper limit of normal by 5 times within 48 hours after surgery; if the blood routine and liver and kidney abnormalities are clinically significant within 48 hours after surgery, and the baseline corresponding examination item is normal or abnormal and it has no clinical significance, review and follow up until abnormalities have no clinical significance.

7.2.3 Device Specification

For the use of the investigational device, the sponsor provides the product's Instruction For Use or User Manual and the Investigator's Brochure and conducts sufficient operation training for all the medical staff involved in the trial during the trial preparation phase to ensure operators are proficient in operating the device.

7.3 Monitoring / Audit plan

Pre-Trial monitoring is mainly divided into: distribution of investigational device to clinical trial sites, preparation of research documents, trial personnel and trial training; In-Trial monitoring is mainly divided into: subjects screening, informed consent, and regular visits, documents to be submitted to the hospital and ethics committee, and monitoring of adverse events; Post-Trial monitoring (or before the termination of the trial) is mainly divided into: recovery of investigational devices, EDC data challenge, confirmation of trial document integrity, Ethics Committee notification, AE and SAE review, closure of sites, clinical trial statistical analysis report and clinical report.

The auditor should undergo the necessary training, be familiar with the Good Clinical Practice for Medical Device and relevant regulations. Also, be familiar with the non-clinical aspects of investigational devices in the trial, as well as the clinical aspects of other similar devices, and clinical trial protocol and related documents.

Each clinical site is visited/inspected at least 2-4 times per week, and the frequency of audits is appropriately increased according to the enrollment situation.

The auditor shall follow the GCP principles and supervise the conduct of clinical trials to ensure that clinical trials are strictly implemented according to the protocol. The trial data is true, complete and accurate. Specific responsibilities

include:

- (1) Confirm prior to trial start that the investigational site has the appropriate conditions, including staffing and training, laboratory equipment in good working conditions, estimated a sufficient number of subjects, participating investigators are familiar with the trial requirements;
- (2) Whether the investigational sites and investigators comply with the approved clinical trial protocol, the Good Clinical Practice for medical device and the relevant regulations before, during and after the trial;
- (3) Confirm that each subject signed an informed consent form prior to participating in the trial. Be aware of subject's inclusion criteria and the progress during the trial. Tests that have not been conducted by the investigators, uncompleted examination, and whether errors or omissions are corrected should be clearly and truthfully recorded. Confirm revised informed consent form is resigned by subjects prior to the end of follow up visit.
- (4) Confirm that all case report forms are correctly filled out and consistent with the original data. All errors or omissions have been corrected or noted and signed and dated by the investigator. The disease type, the total number of cases and the gender, age, and treatment result of each case should be confirmed and recorded;
- (5) Document subjects who withdrawal from the study or is non-compliance with the requirements of the informed consent form. Discuss the situation with the investigator;
- (6) Confirm that all adverse events and device defects should be recorded, and serious adverse events and major device defects that may cause serious adverse events are reported and recorded within the specified time;
- (7) Responsible for monitoring the supply, storage, use, maintenance and handling of medical device samples after the trial;
- (8) Ensure that the relevant equipment is regularly maintained and calibrated and documented during clinical trials;
- (9) Ensure that investigators receive the latest version of all documents related to clinical trials;
- (10) After each audit, a written report shall be sent to the sponsor and investigational site. The report shall state the name of the auditor, the date of the audit, the location of the audit, the content of the audit, the name of the investigator, the completion of the project, problems, conclusions, and corrections to errors, omissions, etc.

8 Statistical Considerations

8.1 Statistical Design, Methodology and Analysis Procedures

8.1.1 Statistical Design (Hypothesis Testing)

This clinical trial is intended to use a prospective, multi-center, single-subject target value design. The main purpose is to evaluate diagnostic consistency rate in diagnosing coronary heart disease by FFRWS measured by investigational device, using FFRPw as the gold standard. Each subject in the clinical trial will provide a pair of test results from both the investigational device and the control device (FFRWS and FFRPw), and the degree of agreement between the two will be used to evaluate the investigational device's performance, using the control product's result as the "gold standard" in the process of comparison (FFRPW \leq 0.80 as positive, FFRPW $>$ 0.80 as negative), evaluating the primary evaluation index ie. accuracy in coronary heart disease diagnosis, applying target values comparison to ensure FFRWS's result satisfies clinical application requirements, the corresponding statistical hypothesis testing is:

$$H_0 : p_T \leq p_0$$

$$H_1 : p_T > p_0$$

p_T represents the investigational device's accuracy in diagnosing coronary heart disease, p_0 represents the target value.

8.1.2 Statistical Analysis Methods

(1) Descriptive Analysis: Describing qualitative data with frequency and composition ratio description; describing quantitative data with mean, standard deviation, maximum, minimum, median, interquartile range, 25th percentile, and 75th percentile.

(2) Baseline demographics statistical analysis: Mainly based on descriptive analysis, comparing subgroups that may be involved, use likelihood ratio χ^2 test between qualitative groups, use Fisher' s exact test when more than 25% of cell frequencies are less than 5; conduct group T-test between normally distributed quantitative datasets; apply Wilcoxon Rank Sum test between non-normally distributed quantitative datasets.

(3) Efficacy analysis: All subjects undergoing a study product review will be included in the analysis (according to the Intention To Diagnostic (ITD)), for the primary efficacy index, in addition to the point estimate for coronary heart disease diagnosis accuracy, the asymptotic normal method and the exact probability method would also be used to make estimates in the 95% confidence interval, comparing the lower bound of the confidence interval with a target value to determine whether the investigational device satisfies clinical application requirements.

(4) Safety evaluation: Adverse events are described by the number and frequency of adverse events; meanwhile, the specific performance, the severity, and the relationship with investigational device of all adverse events will be described in detail.

(5) For primary evaluation indicators, statistical analysis will be conducted with a one-tailed 0.025 significance level, other indicator statistical analysis will be conducted with a two-tailed 0.05 significance level (unless stated otherwise). Statistical analysis is done with SAS®9.4 statistics software.

8.1.3 Statistical Analysis Procedures

Relevant steps in statistical analysis will refer to the provisions of ICH E9 and the relevant guidelines in the "Guidelines for Biostatistics in Clinical Trial" promulgated by the China Food and Drug Administration (CFDA). Meanwhile, all statistical analysis procedures are carried out in strict accordance with the Standard Operating Procedures (SOP) established by the Medical Statistics Department of the National Center for Cardiovascular Diseases.

In addition to the above sample size estimation for the primary endpoint, this clinical trial offers respective statistical considerations for the secondary endpoint. Referencing the target population's positive to negative proportion and the total sample size of 300, in the continuous selected sample, about 100 subjects are tested positive by FFRPW \leq 0.80, while about 200 subjects are tested negative by FFRPW $>$ 0.80. Based on literature reports, set the results from the control device as the gold standard, the sensitivity of the investigational device compared to it is around 86%; the specificity of the investigational device compared to it is around 78%; under the premise that statistical test's two-tailed 0.05 significance level,

current number of positive cases (100) can ensure the error between the sensitivity and the true value of FFRWS is no more than 6.8% (the estimated accuracy is $\pm 6.8\%$); number of negative cases (200) can ensure the error between the specificity and the true value of FFRWS is no more than 5.7% (the estimated accuracy is $\pm 5.7\%$); when the observed sensitivity or specificity of FFRWS is higher than the hypothesized, the estimation accuracy will be further improved..

8.2.2 Number of Clinical Trial per Disease and Reasons for Determination

This clinical trial has tough restrictions on the inclusion/exclusion criteria for selected subjects, it can be considered that the current clinical trial is only conducted for a single indication subject, the above 300 subjects belong to the same disease and will not be further divided.

8.2.3 The Maximum and Minimum Numbers of Subjects Per Clinical Trial

Institution in a Multi-center Clinical Trial and Reasons for Determination

This clinical trial will take place simultaneously in multiple clinical trial institutions, in theory, the number of centers to be grouped will be evenly distributed to ensure maximum representation. But considering the feasibility and progress of selection, the number of enrollment for each institution will be adjusted according to situations. To ensure the balance of each center's selection scale, the final size for any one specific institution will not exceed 50% of the total sample size.

8.3 Clinical Trial's Significance Level and Power

In this clinical trial, the significance level for the statistical analysis is set at two-tailed 5% (unless specified), the test's power is about 90% (only for primary evaluation indexes).

8.4 Expected Drop Out Rate

In the sample size design process, the maximum drop out rate during the clinical trial is expected to be 10%, such drop out rate includes all reasons that prevent a subject from being selected for primary analysis, usually referred to serious violations of clinical trial protocols as determined by researchers (influencing the primary efficacy analysis). Possible scenarios include: a subject does not meet the inclusion criteria, or meets the exclusion criteria; a subject did not use any test-related products; a subject used third-party products outside of clinical trial or such. All of the above will be included in the total drop out rate.

8.5 Criteria for Qualified/Unqualified Results in Clinical Trial

To determine whether a clinical trial result is qualified or not from a statistical standpoint, it is to test the result with the initial hypothesis testing. For this clinical trial, the primary index is the accuracy in coronary heart disease diagnosis, the test results and the preset target values could be compared to determine if the investigational device meets the requirements for clinical application.

In summary, the determination will be based on the comparison between the investigational device's accuracy in coronary heart disease diagnosis and the preset target value. If the result shows: the lower bound of the 95% confidence interval for the investigational device's accuracy in coronary heart disease diagnosis is greater than 75% (the preset target value), then a positive result is obtained, therefore proving the investigational device meets the requirements for clinical application.

8.6 Standards and Reasons for Terminating Clinical Trial Based on Statistical Reasons

This clinical trial does not have preset interim analysis and corresponding standards for early termination, thus it is not applicable here. All statistical analysis will be performed after the data has been collected, cleaned, and finally locked in.

8.7 Statistical Methods of All Data, Along With Missing, Unused, and Erroneous Data (Including Withdrawals) and the Processing Methods for Unreasonable Data

The statistical analysis processes (procedures) are carried out in strict accordance with the Standard Operating Procedures (SOP) established by the Medical Statistics Department of the National Center for Cardiovascular Diseases. Details can be referred to related documents.

To account for possible missing data in clinical trials, the missing primary endpoint index will be carried over during analysis, the specific carry over procedure will be outlined in the statistical analysis plan, if there exists any missing results, it will be treated as inconsistent in the consistency evaluation. No carry-over processing will be done on other missing index, analysis will be performed on observed data.

Erroneous and unreasonable data will be cleaned in the data cleansing process before statistical analysis. The information of subjects who withdrew from clinical trials will still be included in the final statistical analysis. The specific reasons for

withdrawal of each subject will be described in the statistical report, the missing primary index caused by early withdrawal will be carried over following the above missing value processing method.

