- Device success rate: Taking the blood vessel as the research unit, effective FFR_{WS} and FFR_{PW} readings will be used as the criteria to judge the success rate of the devices, and the success rate of the investigational device and the control device will be compared.

7.1.6.2 Methods and time selection for evaluating, documenting and analyzing effectiveness parameters

(1) Primary effectiveness endpoint: the consistency rate in the diagnosis of coronary heart disease with investigational device and control device.

At Visit 2(FFR-ICA examination), record coronary artery FFR_{WS} measured by investigational device and coronary artery FFR_{PW} measured by control device. After all subjects completed the Visit 2, taking the subject as the research unit, the consistency

rate of investigational device for diagnosis of coronary heart disease will be calculated based on FFR_{WS} measured by investigational device. FFR_{PW} of coronary artery measured by control device will be used as the reference and $FFR_{PW} \leq 0.80$ as positive threshold.

Diagnostic consistency rate = (true positive + true negative) / (positive + negative);

Positive and negative respectively correspond to the results of the control device assay (positive when $FFR_{PW} \leq 0.80$, negative when $FFR_{PW} > 0.80$), true positive refers to that when investigational device is also positive at the same time as control device is positive ($FFR_{PW} \leq 0.80$ and $FFR_{WS} \leq 0.80$, true negative refers to that when control device is negative and investigational device is also negative ($FFR_{PW} > 0.80$ and $FFR_{WS} > 0.80$).

(2) Secondary effectiveness endpoint:

➤ Sensitivity and specificity of investigational device in the diagnosis of coronary heart disease:

At Visit 2 (FFR-ICA examination), record the coronary artery FFR_{WS} measured by investigational device and the coronary artery FFR_{PW} measured by control device. After all subjects completed the visit 2, taking the subject as the research unit, the sensitivity and specificity of investigational device for diagnosis of coronary heart disease will be calculated based on FFR_{WS} measured by investigational device. FFR_{PW} of coronary artery measured by control device will be used as the reference and $FFR_{PW} \leq 0.80$ as positive threshold.

Sensitivity = True Positive / Positive;

Specificity = True Negative / Negative;

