8.9 Standards and Reasons for Selecting Subjects to be included in the Analysis

Statistical analysis will be performed upon the following demographics, demographic categorization will be done prior to the statistical analysis, the analysis population in this clinical trial includes:

Full Analysis Set (FAS): collection of subjects selected based on the Intention To Diagnostic (ITD) principles, refers to the dataset of all subjects who participated in the research and used the investigational device.

Per Protocol Set (PPS): the subgroup of the subjects who completed the trial, excluding those who seriously violated the procedure (refers to the trial subjects who violated the selection standard or the exclusion standard, or those lost during the trial).

Safety Set (SS): Use the same definition method as the Full Analysis Set (FAS), therefore the Safety Set will not be defined separately in the analysis.

The analysis of primary efficacy index will be performed on the Full Analysis Set (FAS) and the Per Protocol Set (PPS); in addition, all baseline demographic data and secondary efficacy analysis will be performed on the Full Analysis Set (FAS), the safety evaluation will also be performed on the Full Analysis Set (FAS).

8.10 Exclusion of Special Information during Hypothesis Verification and Its Reasons (If Applicable)

Not applicable.

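### Section 8.7's observed-data rule, on its natural reading, drops investigational-device failures from sensitivity and specificity, which the primary endpoint's missing-data rule and the control-based denominators do not do

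*Combined protocol and SAP*

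**What the plan says.** Section 8.7 sets two rules. For the primary endpoint, "if there exists any missing results, it will be treated as inconsistent in the consistency evaluation". For everything else, "No carry-over processing will be done on other missing index, analysis will be performed on observed data". Sensitivity and specificity are subject-level secondary endpoints (section 7.1.6.1), so the second rule governs them.

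Three other places bear on the same subjects:

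- Section 7.1.6.2 gives the formulas "Sensitivity = True Positive / Positive" and "Specificity = True Negative / Negative". Under the primary endpoint, the same section ties positive and negative to the control device's result.
- Section 8.9 places secondary efficacy on the Full Analysis Set (FAS). It defines that set by the intention-to-diagnose principle, as all participants in whom the investigational device was used.
- Section 8.1.2 says of the efficacy analysis: "All subjects undergoing a study product review will be included in the analysis".

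No section says how a subject with a control reading but no valid investigational reading enters the two-by-two table.

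**The concern.** A subject in whom the investigational wire was used but gave no valid reading is in the FAS. If the control wire gave a reading, that subject's reference class is known, so the subject can be counted in sensitivity or specificity. An observed-data analysis leaves the subject out.

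The plan foresees such failures. It makes an effective reading the criterion of device success (sections 7.1.6.2 and 7.2.1.2), cautions about invalid FFR in the operating directions (section 7.1.4), and names wire breakage (section 10.2) and malfunction (section 13.3).

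Two things are at stake. First, the investigational device's own failures would count against it in the primary endpoint and disappear from sensitivity and specificity, always in the device's favour. Second, the primary and secondary results would rest on different subjects with no rule to explain the difference. Section 8.2.1 gives sensitivity and specificity their own precision justification, so they will be read as substantive results.

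**Working it through.** **Inputs.** From section 8.2.1: sensitivity about 86%, specificity about 78%, about 100 control-positive and 200 control-negative subjects, stated precision ±6.8% and ±5.7% at two-sided 0.05. The subject-level failure rate f of the investigational device is not in the documents. It is an assumption here, taken as 1% to 8% and equal in control-positives and control-negatives. The 86% and 78% are treated as the values among subjects with a valid reading.

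**The plan's own figures.** Half-width = 1.96 × √(p(1−p)/n).

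- Sensitivity: 1.96 × √(0.86 × 0.14/100) = 6.80%.
- Specificity: 1.96 × √(0.78 × 0.22/200) = 5.74%.

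Both reproduce.

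**Direction.** Let P be the control-positives, m of them without a valid FFR_WS, and TP the true positives. Observed-data sensitivity is TP/(P−m). With failures kept and counted as incorrect it is TP/P. Since m ≥ 0, the first is never smaller, and with f = m/P it is larger by the factor 1/(1−f). The same holds for specificity.

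**Size.** Failures kept: 86% × (1−f) and 78% × (1−f).

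| Assumed f | Sensitivity, failures dropped | Sensitivity, failures incorrect | Specificity, failures dropped | Specificity, failures incorrect |
|---|---|---|---|---|
| 1% | 86.0% | 85.1% | 78.0% | 77.2% |
| 2% | 86.0% | 84.3% | 78.0% | 76.4% |
| 5% | 86.0% | 81.7% | 78.0% | 74.1% |
| 8% | 86.0% | 79.1% | 78.0% | 71.8% |

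At 5% the gaps are 4.3 and 3.9 points, about two thirds of the stated precision (4.3/6.8 = 0.63; 3.9/5.7 = 0.68). At 1% both are below one point.

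**Reconciliation with the primary endpoint.** At f = 5%, 95 control-positives are evaluable with 81.7 expected true positives, and 190 control-negatives with 148.2 expected true negatives.

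- Agreement on evaluable subjects: (81.7 + 148.2)/285 = 80.7%.
- Agreement under the primary rule: (81.7 + 148.2)/300 = 76.6%.

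The 80.7% is only the weighted mean of the planning sensitivity and specificity. It is not the 83% accuracy assumed for the sample size.

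**PPV and NPV.** Section 7.1.6.2 defines them as TP/(TP+FP) and TN/(TN+FN). At f = 5%, PPV = 81.7/(81.7 + 41.8) = 66.2% and NPV = 148.2/(148.2 + 13.3) = 91.8%, the same as with no failures. A failed reading belongs in neither denominator. These values fall only if each failure is forced to the wrong call.

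**The case against.** The strongest reply is that section 8.7 does not say failures are excluded; it only rules out carry-over for the other endpoints. With positive and negative tied to the control result, a literal reading of the section 7.1.6.2 formulas keeps a failed subject in the denominator without a true result, which is what the fix asks for. This stands in part. A reader might infer that the plan expressly removes these subjects, but the text only implies it. What is left is a conflict between sections, with the observed-data wording the more natural guide for an analyst.

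A second reply is that the intention-to-diagnose sentence in section 8.1.2 runs straight on to the primary index and may govern only that. This is fair, but section 8.9 carries the same principle into the FAS and assigns secondary efficacy to it. The FAS definition settles who belongs and not how missing values are handled, so the gap remains.

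Third, failures are disclosed as the device success rate and compared between devices. That is so, but by vessel. It shows neither how many subjects lack a result nor their control class, so sensitivity and specificity cannot be rebuilt from it.

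Fourth, the size is unknown. The failure rates are assumptions, and 86% and 78% are planning values from literature, not results. In a subject with several lesions, one failed vessel need not mean no subject-level result; section 7.1.6.1 leaves that conversion to the statistical analysis plan. All of this stands.

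**Conclusion.** The point holds for sensitivity and specificity. On the natural reading of section 8.7, subjects with a valid FFR_PW and no valid FFR_WS drop out, against the control-based denominators, the FAS principle and the plan's own primary rule. The direction is certain: equal or higher. The size depends on a failure rate the documents do not give. It is under one point at 1%, and about 4 points at 5% if failures are equally frequent in both control classes.

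Three stronger conclusions that a reader might draw are not supported:

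- That PPV and NPV are inflated too. They are conditional on a test result, so leaving failures out is their ordinary definition.
- That the trial's success decision is affected. Section 8.5 rests it on the primary endpoint alone, where a missing result already counts against the device.
- That the fix would make the primary and secondary tables agree fully. The primary rule also counts a missing FFR_PW as inconsistent, and those subjects have no reference class for sensitivity or specificity.

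**What to change.** In section 8.7 and the statistical analysis plan, state that:

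- for sensitivity and specificity, a FAS subject with a valid FFR_PW and no valid subject-level FFR_WS stays in the denominator and counts as incorrect;
- the observed-data (evaluable) version is reported as a supporting table;
- the number of subject-level investigational failures is shown by control result;
- PPV and NPV are computed on subjects with a valid test result;
- subjects with a missing FFR_PW are listed separately, as the explanation of any remaining difference from the primary denominator.

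Section 8.8 allows recorded adjustments until the analysis plan is finalised before database lock. Settling the rule by then means it is not left to the analyst's interpretation afterwards. The cost is a short addition to the text, one extra table and slightly less favourable secondary estimates. No new data are needed, and the sample size and primary decision are unchanged.
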